### 7.1.2 GRADING AND RELATIONSHIP TO DRUG

The descriptions and grading scales found in the CTEP Version 4 of the NCI Common Terminology Criteria for Adverse Events (CTCAE) will be utilized for AE reporting. CTEP Version 4 of the CTCAE is identified and located at: [http://ctep.cancer.gov/protocolDevelopment/electronic\\_applications/ctc.htm](http://ctep.cancer.gov/protocolDevelopment/electronic_applications/ctc.htm). AEs not covered by specific criteria should be reported with common medical terminology and graded according to definitions provided in the CTCAE Version 4.

AEs NOT listed in the NCI-CTCAE, the severity of AEs will be graded as follows:

- **Grade 1 – Mild:** Event barely noticeable to subject; no limitation in activity, no minimal medical intervention/therapy required.
- **Grade 2 – Moderate:** Event of a sufficient severity to make participant uncomfortable. ADL limited; no or minimal medical intervention/therapy required.
- **Grade 3 – Severe:** Event causes significant discomfort/limitation in activity. May be such severity that the subject cannot continue on study. Severity may cause cessation of treatment. Treatment for symptoms may be given and/or subject hospitalized.
- **Grade 4 - Life Threatening:** Event places the participant at immediate risk of death from the reaction as it occurred. Significant medical intervention/therapy required; hospitalization or hospice care probably.
- **Grade 5 - Death.**

The relationship of event to study drug will be documented by the Investigator as follows:

- **Unrelated:** The event is clearly related to other factors such as the subject’s clinical state, other therapeutic interventions or concomitant drugs administered to the subject.

- **Unlikely:** The event is doubtfully related to investigational agent(s). The event was most likely related to other factors such as the subject's clinical state, other therapeutic interventions, or concomitant drugs.
- **Possible:** The event follows a reasonable temporal sequence from the time of drug administration, but could have been produced by other factors such as the subject's clinical state, other therapeutic interventions or concomitant drugs.
- **Probable:** The event follows a reasonable temporal sequence from the time of drug administration, and follows a known response pattern to the study drug. The event cannot be reasonably explained by other factors such as the subject's clinical state, therapeutic interventions or concomitant drugs.
- **Definite:** The event follows a reasonable temporal sequence from the time of drug administration, follows a known response pattern to the study drug, cannot be reasonably explained by other factors such as the subject's condition, therapeutic interventions or concomitant drugs; AND occurs immediately following study drug administration, improves upon stopping the drug, or reappears on re-exposure.

A suspected adverse reaction is any AE for which there is a reasonable possibility that the drug caused the adverse event. Reasonable possibility means there is evidence to suggest a causal relationship between the drug and the adverse event, such as:

- A single occurrence of an event that is uncommon and known to be strongly associated with drug exposure (e.g., angioedema, hepatic injury, Stevens-Johnson Syndrome).
- One or more occurrences of an event that is not commonly associated with drug exposure, but is otherwise uncommon in the population exposed to the drug.
- An aggregate analysis of specific events observed in a clinical research study that indicates those events occur more frequently in the drug treatment group than in a concurrent or historical control group.

An AE for which there is a reasonable possibility that the drug caused the adverse event includes those assessed as having a Possible, Probable, or Definite causality assessment.

### 7.1.3 REPORTING ADVERSE EVENTS

**Table 1. Guidelines for Routine Adverse Event Reporting for Pilot Studies (Regardless of Expectedness)**

Attribution	Grade 1	Grade 2	Grade 3	Grade 4	Grade 5
Unrelated	X	X	X	X	X
Unlikely	X	X	X	X	X
Possible	X	X	X	X	X
Probable	X	X	X	X	X
Definite	X	X	X	X	X

All subjects are evaluated at baseline and any abnormalities are documented.

- Worsening abnormalities and/or worsening of a pre-existing condition (e.g., diabetes, migraine that has increased in severity, frequency or duration of the condition, or an association with significantly worse outcome) can become an AE or serious adverse event and must be documented and followed.
- A persistent AE is one that extends continuously, without resolution between treatment cycles/courses. Reporting of persistent AEs is as follows:
  - a) Routine reporting: The AE must be reported only once unless the grade becomes more severe in a subsequent cycle/course. If the grade becomes more severe the AE must be reported again with the new grade.
  - b) Expedited Reporting: the AE must be reported only once unless the grade becomes more severe in the same or a subsequent cycle/course.
- A recurrent AE is one that occurs and resolves during a cycle/course of therapy and then reoccurs in a later cycle/course. Reporting of recurrent AEs is as follows:
  - a) Routine Reporting: An AE that resolves and then recurs during a subsequent cycle/course must be reported by the routine procedures.
  - b) Expedited Reporting: An AE that resolves and then recurs during a subsequent cycle/course does not require reporting unless the grade increases and hospitalization is associated with the recurring AE.
- At each evaluation, the Investigator will determine whether any AEs have occurred by evaluating the subject's signs, symptoms, and current laboratory and/or other test results.
- All AEs (expected or unexpected), including worsening of a pre-existing conditions (increased severity, frequency or duration of the condition and/or associated with significantly worse outcomes) which occur during the specified collection period, whether observed by the Investigator or by the subject, and whether or not thought to be related to study drug, will be documented in detail and followed until resolution, stabilization, death, or the start of new treatment.
- Whenever possible record a diagnosis for signs and symptoms of a common syndrome (i.e., cough, sneezing, runny nose would be reported as an upper respiratory infection).

All AEs for Pilot studies must be entered on the Adverse Event eCRF page, using the pTrax database.

## 7.2 SERIOUS ADVERSE EVENTS

### 7.2.1 DEFINITION

A serious adverse event (SAE) is any adverse event (experience) that in the opinion of either the investigator or sponsor results in **ANY** of the following:

- Death.
- A life-threatening adverse event (experience). Any AE that places a subject or subject, in the view of the Investigator or sponsor, at immediate risk of death from the reaction as it occurred. It does **NOT** include an AE that, had it occurred in a more severe form, might have caused death.
- Inpatient hospitalization or prolongation of existing hospitalization (for > 24 hours).
- A persistent or significant incapacity or substantial disruption of the ability to conduct normal life functions.
- A congenital anomaly or birth defect.
- Important Medical Event (IME) that, based upon medical judgment, may jeopardize the subject or subject and may require medical or surgical intervention to prevent one of the outcomes listed above.

Elective hospital admission (including planned treatment for progressive disease or a planned protocol procedure), admission for socioeconomic reasons, and death due to tumor progression will not be considered an SAE.

All SAEs will be collected from the date of subject or subject signing consent until 30 days after the last dose of study drug and/or procedure.

## **7.2.2 REPORTING SERIOUS ADVERSE EVENTS**

AE may be identified as an Unanticipated Problem by the Investigator. Please refer to **Section 7.3.2** for details on reporting Unanticipated Problems.

The SAE Form should be completed with all available information, including a brief narrative describing the adverse event and any other relevant information. If applicable, the narrative must also include identification of similar reports and an analysis of the significance of the AE.

## **7.2.3 FOLLOW-UP FOR SERIOUS ADVERSE EVENTS**

All SAEs will be followed until resolution, stabilization, death, or the start of new treatment.

## **7.3 UNANTICIPATED PROBLEMS**

### **7.3.1 DEFINITION**

An Unanticipated Problem (UP) is any incident, experience, or outcome that meets all of the following criteria:

- Unexpected (in terms of nature, severity, or frequency) given:

- The research procedures that are described in the study-related documents, including study deviations, as well as issues related to compromise of subject privacy or confidentiality of data.
- The characteristics of the subject population being studied.
- Related or possibly related to participation in the research (possibly related means there is a reasonable possibility that the incident, experience, or outcome may have been caused by the procedures involved in the research).
- Suggests that the research places subjects or others at a greater risk of harm (including physical, psychological, economic, or social harm) than was previously known or recognized and if in relation to an AE is also deemed **Serious** per **Section 7.2**.

### **7.3.2 REPORTING UNANTICIPATED PROBLEMS**

SAEs that are serious, unexpected and for which there is a reasonable possibility that the study drug caused the adverse event are reported on the Unanticipated Problem Form and submitted to CRS Compliance Office within 24 hours of becoming aware of the Unanticipated Problem.

Within 5 business days, an Unanticipated Problem Form should be completed with all available information, including a brief narrative describing the unanticipated problem and any other relevant information.

Within 5 business days of becoming aware of new information about the Unanticipated Problem, submit this updated information to CRS Compliance with an updated UP Form.

## **8 DATA AND SAFETY MONITORING**

The Data Safety Monitoring Plan is attached in the IRB. The study members will meet monthly to ensure that standard procedures are being followed.

## **9 STATISTICAL METHODOLOGY**

Initially ten patients will be treated to determine the feasibility of HIVM for deep space tumors. This first part of the study is a pilot study of feasibility. If seven or more patients are deemed a success by meeting all of the criteria below, then HIVM will be deemed feasible in the study of deep space tumors. Criteria include the ability to complete each of the following:

1. Identify and measure vessels associated with tumor
2. Determine vessel density per 10x field
3. Visualize vital dyes within the vessels (fluorescein)
4. Calculate the blood flow velocity of the vessels and tissue penetration of fluorescein as a marker of vessel permeability.

If the true success rate is 60%, the probability of deeming HIVM feasible is 63%; if the true success rate is 70%, then the probability of deeming HIVM feasible is 88%; and if the true success rate is 90%, then the probability of deeming HIVM feasible increases to 99%.

If HIVM is deemed feasible, then an additional 40 patients will be accrued to this study in order to address the following:

1. Post-operative comparison of the microvasculature of tumor with normal tissue (peritoneum) in each individual subject using vessel diameters, vessel density, detection of intravital dye and flow rates.
2. Post-operative correlation of the microvasculature with pathologic features of the tumor (i.e. tumor grade) at the time of the final pathology report (5-7 days after surgery).
3. Post-operative correlation of the microscopic observation of the tumor microvasculature tumor-specific and overall survival.

An abnormal HIVM observation is defined by any of the following criteria:

1. Aberrant vessel structure compared to normal tissue, which includes tortuosity of the vessel wall or a closed loop formation.
2. Aberrant vessel branching patterns compared to normal tissue, which includes erratic and disorganized branching points.
3. Blood vessel density that is less than or greater than one standard deviation of the blood vessel density observed in normal tissue.
4. Inability to detect flow or fluorescein within a vessel.
5. Average blood flow rate through observed vessel that is less than one standard deviation of the average blood flow rate through a normal vessel.

A matched analysis will be performed for observations of microvasculature between the tumor and normal tissue. For dichotomous variable comparisons between vessel structure (normal vs aberrant), vessel branching patterns (normal vs aberrant), or detection of intravital dye (present vs absent), a McNemar's test will be performed. For continuous variable comparisons between blood vessel density and average blood flow rate, a paired t test will be performed.

Associations between characteristics for the baseline (normal peritoneal microvasculature observed surrounding the tumor) and tumor itself will be depicted with graphics, correlations, and model results.

Similar analyses will be performed to compare baseline observations with those performed after fluid bolus and/or vasopressor administration.

Adverse event and complication rates will be described using upper one-sided 95% Clopper Pearson confidence limits.

Overall survival will be defined as the duration of time from diagnosis to time of death. Disease specific survival will be defined as the time from surgery to death due to recurrence. Overall survival and disease specific survival will be generated using standard Kaplan-Meier methodology.

A maximum of 50 subjects will be enrolled in this study (initially 10 to determine feasibility and then 40 additional subjects if deemed feasible). The accrual rate is estimated at 1-2 subjects per month, and the estimated study duration is 30 months (2.5 years).

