*Primary objective(s):* To determine the feasibility of performing HIVM in patients with deep space solid tumors during standard course of surgical resection. A successful intravital microscopic observation will include the ability to complete each of the following:

1. Identify and measure vessels associated with tumor
2. Determine vessel density per 10x field
3. Visualize vital dyes within the vessels (fluorescein)
4. Calculate the blood flow velocity of the vessels and tissue penetration of fluorescein as a marker of vessel permeability.
5. Obtain these vessel parameters after administration of an IV fluid bolus and/or vasopressor administration (phenylephrine or vasopressin) during the normal course of the surgical resection.

*Secondary objective(s):*

1. Compare the microscopic observation of the tumor-associated vessels with normal tissue (e.g. peritoneal surface) in each individual subject.
2. Correlate the microscopic observations of the tumor-associated vessels with pathologic grade of tumor.
3. To correlate the microscopic observation of the microvasculature with tumor-specific and overall survival.

Study Design: This is a non-randomized, single center, study of HIVM observation in subjects with deep space solid tumors undergoing surgical resection.

All subjects will meet the inclusion and exclusion criteria prior to participation in this study. Standard evaluation by the Preoperative Anesthesia clinic at Mayo Clinic Florida may include additional testing such as EKG, chest x-ray, and/or pulmonary function tests.

The study will be performed in two parts. Part 1 will enroll 10 patients with an expected feasibility rate of 70%. Whereas the feasibility rate in primary melanoma was 90%, the expected feasibility rate for deep space tumors may be lower as the site is in an anatomically deeper location. If Part 1 is not met (i.e. in three or more patients), the primary objective would not be considered technically feasible, and then the study will be stopped. If Part 1 is fulfilled, then the study will continue with an additional 40 patients enrolled (total of 50 patients). Accrual is expected to take 2.5 years.

*Inclusion criteria:*

1. Age  $\geq$  18 years of age.
2. ECOG Performance Status of  $\leq 2$ .
3. Measurable tumor by direct visualization requiring surgical resection in the OR.

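### Two of the three stated probabilities of passing the feasibility gate do not belong to the 7-of-10 rule: at the expected 70% rate the gate passes 65% of the time, not 88%

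*Combined protocol and SAP*

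**What the plan says.** Section 9 (Statistical Methodology) sets the size of Part I: "Initially ten patients will be treated to determine the feasibility of HIVM for deep space tumors". It sets the decision rule: "If seven or more patients are deemed a success by meeting all of the criteria below, then HIVM will be deemed feasible". It then gives three probabilities of passing:

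- "If the true success rate is 60%, the probability of deeming HIVM feasible is 63" per cent;
- "if the true success rate is 70%, then the probability of deeming HIVM feasible is 88" per cent;
- "if the true success rate is 90%, then the probability of deeming HIVM feasible increases to 99" per cent.

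The gate decides whether Part II takes place: "If HIVM is deemed feasible, then an additional 40 patients will be accrued to this study".

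The synopsis (Study Design) gives the planning assumption: "Part 1 will enroll 10 patients with an expected feasibility rate of 70" per cent. It also says that the study stops if Part 1 is not met. Section 4.2 replaces patients lost to equipment faults or to unrelated termination of surgery and does not count them as failures, so the denominator stays at ten.

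**The concern.** The rule and the probabilities stand in the same section and should determine each other, because ten patients and a cutoff of seven fix the pass probability at any true rate. A figure of 88% at a true rate of 70% cannot be right on its face. The expected number of successes is then 10 × 0.70 = 7, exactly the cutoff, so the chance of reaching it should be somewhat above one half.

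These are the only numerical operating characteristics in the plan, and they describe its only stop/go decision. Anyone who judged the gate from Section 9 would believe that a technique performing as expected would be abandoned about one time in eight. They would also believe that a technique running below expectation, at 60%, would usually pass.

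**Working it through.** **Inputs.** n = 10 and cutoff 7 (Section 9); true rates 60%, 70% and 90% with stated probabilities 63%, 88% and 99% (Section 9); expected rate 70% (synopsis, Study Design). Patients are taken as independent with a common success probability p.

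**Formula.** P(pass) = P(X ≥ 7) = Σ C(10, k) p^k (1 − p)^(10 − k), summed over k = 7 to 10.

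**Attempt to reproduce the stated figures.**

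| True rate | k = 7 | k = 8 | k = 9 | k = 10 | P(X ≥ 7) | Stated | Stated minus exact |
|---|---|---|---|---|---|---|---|
| 60% | 0.2150 | 0.1209 | 0.0403 | 0.0060 | 0.3823 | 0.63 | +25 points |
| 70% | 0.2668 | 0.2335 | 0.1211 | 0.0282 | 0.6496 | 0.88 | +23 points |
| 80% | 0.2013 | 0.3020 | 0.2684 | 0.1074 | 0.8791 | not given | – |
| 90% | 0.0574 | 0.1937 | 0.3874 | 0.3487 | 0.9872 | 0.99 | agrees |

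(The four terms are rounded, so a row may differ from its sum by 0.0001.)

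**Chance of failing the gate at the expected rate.** 1 − 0.6496 = 0.3504, about one in three. The stated figure implies 1 − 0.88 = 0.12, about one in eight.

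**Could another rule or method explain the figures?**

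| Variant (n = 10) | 60% | 70% | 90% |
|---|---|---|---|
| Stated | 63% | 88% | 99% |
| 6 or more | 63.3% | 85.0% | 99.8% |
| 7 or more (as written) | 38.2% | 65.0% | 98.7% |
| 8 or more | 16.7% | 38.3% | 93.0% |
| 7 or more, normal approximation with continuity correction | 37.3% | 63.5% | 99.6% |
| 7 or more, normal approximation without correction | 25.9% | 50.0% | 98.3% |

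No row gives all three stated values. A search over every n from 1 to 60 and every cutoff finds no design with both 63% at 60% and 88% at 70%. The nearest is 10 or more of 17, at 64.1% and 89.5%, which is not the design described.

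**Possible origin.** The 63% equals the 6-of-10 probability at a true rate of 60%. The 88% equals the 7-of-10 probability at a true rate of 80%. The figures may therefore have been read from different cutoffs or different true rates. This is inference; the documents do not show how the figures were obtained, and the error does not depend on it.

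**The case against.** The strongest objection is that the cutoff itself is not settled, so the 35% is conditional. The synopsis says: "If Part 1 is not met (i.e. in three or more patients), the primary objective would not be considered technically feasible". If that means three failures stop the study, continuing needs eight or more successes. At a true rate of 70% the gate would then pass 38.3% of the time and stop 61.7% of the time. This stands as a separate inconsistency: the two sections would disagree at exactly seven successes and need reconciling. It does not rescue the stated figures, because 88% is further off under an 8-of-10 rule than under 7 of 10.

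It can also be said that the documents do not show which element is wrong: the probabilities, the true rates printed beside them, or the cutoff. That is fair. The correction below follows the rule as Section 9 writes it, and a different intended cutoff would need its own figures.

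Finally, Part I is a pilot gate with no hypothesis test, and the decision is made by counting successes, so a wrong probability changes no patient's observation and no go/no-go outcome. That is true. The harm is that the sponsor and the review board are misinformed about the risk of stopping. Having chosen to state exact probabilities for a binding rule, the plan should state the ones that belong to it.

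**Conclusion.** The concern holds. Under the 7-of-10 rule in Section 9, the probability of deeming HIVM feasible is 38.2% at a true rate of 60% (stated 63%), 65.0% at 70% (stated 88%) and 98.7% at 90% (stated 99%, correct). At the sponsor's expected rate the chance of failing the gate is 35.0%, nearly three times the implied 12%. At 60% the rule is stricter than the plan says. The errors are far beyond rounding and arise under no single design with up to 60 patients. The result assumes independent patients with a common success probability, a denominator held at ten by replacement, and the Section 9 cutoff.

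**What to change.** Replace the probability sentence in Section 9 with the exact values for seven or more successes in ten: 38% at a true rate of 60%, 65% at 70%, 88% at 80% and 99% at 90%. State beside it that the chance of stopping at the expected 70% rate is 35%.

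In the same edit, confirm that seven of ten is the intended cutoff and bring the synopsis wording on three or more patients into line with it.

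If the sponsor finds a 35% stopping risk too high, that should be decided openly and recorded. For comparison only, a 6-of-10 cutoff passes 63%, 85% and 99.8% of the time at 60%, 70% and 90%.

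**Cost.** Correcting the figures takes one sentence and no extra patients; the stated properties become less favourable. Aligning the synopsis takes one more phrase. Changing the cutoff would be a protocol revision needing IRB approval under Section 12.1.

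### Aberrant structure and branching are defined against normal tissue and then compared with normal tissue by McNemar's test, which biases both tests toward tumor

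*Combined protocol and SAP*

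**What the plan says.** All the relevant text is in Section 9 (Statistical Methodology). A list of five criteria opens with "An abnormal HIVM observation is defined by any of the following criteria". The first criterion is "Aberrant vessel structure compared to normal tissue, which includes tortuosity of the vessel wall or a closed loop formation" and the second is "Aberrant vessel branching patterns compared to normal tissue, which includes erratic and disorganized branching points". Each one ties the call to normal tissue and also names visible features.

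The analysis text then states: "A matched analysis will be performed for observations of microvasculature between the tumor and normal tissue". The dichotomous variables are "vessel structure (normal vs aberrant), vessel branching patterns (normal vs aberrant), or detection of intravital dye (present vs absent"), and for these "a McNemar's test will be performed". The normal tissue is described as the baseline, namely "normal peritoneal microvasculature observed surrounding the tumor".

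Section 4.2 has observations taken over 2-4 areas of both grossly normal and tumor tissue. Its off-line analysis covers diameter, velocity, shear rate, density and dye uptake, but gives no rule for scoring structure or branching. The documents do not say how a normal field is scored on these two variables, whether the reference is the patient's own tissue or a pooled one, or whether readers are blinded to tissue type. For the McNemar comparison they give no alpha, sidedness, test version or expected discordance.

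**The concern.** McNemar's test asks whether tumor-only aberrant pairs and normal-only aberrant pairs are equally frequent. The question has content only if either tissue can be called aberrant. If aberrant means different from the patient's normal tissue, the normal member of each pair is its own reference and cannot differ from itself. The normal-only cell is then empty because of the definition, whatever the vessels look like.

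A positive result on structure or branching could then partly restate the definition. It would also be easy to believe, because Section 1 (Background) already presents irregular branching and anastomotic structures as characteristic of tumor vessels. Two of the three McNemar variables are exposed.

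**Working it through.** **Inputs.** From the documents: a maximum of 50 patients, of whom 40 are in Part II. Section 9 says the additional 40 are accrued to address the tumor-normal comparison, so both numbers are shown. Assumed, because the documents give no figure: two-sided alpha 0.05 and the feature rates below. The plan has no power or error figure for this test, so there is none to reproduce.

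**Step 1: smallest significant result.** Let b be the number of tumor-only aberrant pairs and c the number of normal-only aberrant pairs. On the literal reading c = 0.

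- Exact two-sided: p = 2 × 0.5^b. b = 5 gives 0.0625; b = 6 gives 0.031.
- Uncorrected chi-square: b²/b = b on 1 df. b = 3 gives p = 0.083; b = 4 gives p = 0.0455.
- Continuity-corrected: (b − 1)²/b. b = 6 gives 25/6 = 4.17, p = 0.041; b = 5 gives p = 0.074.

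The exact test therefore needs 6 one-way pairs, which is 6/50 = 12% or 6/40 = 15% of patients. The uncorrected test needs 4.

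**Step 2: chance of reaching 6.** Let q be the share of patients scored tumor aberrant and normal tissue normal. The chance of exact p<0.05 is P(B ≥ 6) with B ~ Binomial(n, q).

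| One-way rate q | n = 50 | n = 40 |
|---|---|---|
| 5% | 3.8% | 1.4% |
| 10% | 38% | 21% |
| 12.75% | 63% | 40% |
| 16% | 83% | 63% |
| 20% | 95% | 84% |
| 30% | 99.9% | 99.1% |

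**Step 3: what q is when the tissues do not differ.** Suppose a feature is present at the same rate r in tumor and in normal tissue, independently within patients. A tumor whose own peritoneum shows the same feature is not aberrant relative to it, so those pairs drop out and q = r(1 − r). For r = 15%, q = 0.15 × 0.85 = 12.75%. For r = 20%, q = 0.20 × 0.80 = 16%. The table gives 63% and 83% at n = 50, and 40% and 63% at n = 40. If the features coincide more often within a patient, q falls; with complete agreement it is 0 and so is the chance of significance.

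**Step 4: the same case under a common rule.** If the feature is scored by one rule in both tissues, with equal and independent rates, c is free and equals b in expectation. The exact two-sided test then rejects in 2.1%, 2.8%, 3.0% and 3.0% of trials at r = 10%, 20%, 30% and 50% with n = 50. With n = 40 the figures are 1.7%, 2.5%, 2.9% and 3.0%. Error stays below 5% throughout.

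**The case against.** The strongest reply is that the plan need not be read literally. Tortuosity, closed loops and disorganized branching can be looked for in any field. A matched analysis with a normal/aberrant value for each tissue presupposes that normal fields are scored too. The comparison with normal tissue may mean departure from typical normal vasculature, in which case an individual peritoneal field could be aberrant. The five criteria also define an abnormal observation, and Section 9 does not say outright that the McNemar variables inherit that wording. All of this stands as a possible reading. The documents do not choose it, however, and they contain no other definition of aberrant structure or branching for the analysis to use.

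A reader might go further and infer that the tests are significant by construction. They are not. Only the direction is fixed; at a 5% one-way rate the chance of exact significance is 3.8% with 50 pairs. Nor does it follow that equal feature rates in both tissues always produce a positive result, since the outcome depends on within-patient agreement. It would also be wrong to put all 15% of tumors into the discordant cell when the features are equally common: that gives 78% at n = 50 but ignores the pairs in which both tissues show the feature.

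The reach is limited too. Secondary endpoint 1 in Section 3.3 lists diameters, density, dye detection and flow rates, and does not list structure or branching. Dye is scored present or absent without reference to normal tissue, and density and flow are compared by paired t test. This part of the objection stands in full.

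**Conclusion.** The concern holds in limited form. As worded, Section 9 uses the comparator to define the outcome and gives no common scoring rule for the two tissues, so the McNemar tests on structure and branching are biased toward tumor on the literal reading. With equal, independent feature rates of 15%, the chance of a false exact p<0.05 is about 63% with 50 pairs and 40% with 40, against 2 to 3% under a common rule at the rates checked (10% to 50%). The size rests on four assumptions: the patient's own peritoneum is the reference, alpha is 0.05 two-sided, the feature rate is as chosen, and the tissues are independent within patients. Across one-way rates of 5% to 20% it runs from 3.8% to 95% at n = 50.

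The effect is confined to two qualitative descriptors. The dye, density and flow comparisons and the primary feasibility endpoint are untouched. The wording should be corrected before the videos are scored.

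**What to change.** Delete the comparison with normal tissue from criteria 1 and 2 in Section 9. State that three features (tortuous wall, closed loop, erratic or disorganized branching) are scored present or absent by the same rule in every tumor and every normal field, so that a normal field can also be scored aberrant. Run McNemar's test on those scores, and state alpha, sidedness and whether the test is exact. Having readers score without knowing the tissue type, where the images allow it, would be a sensible addition.

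The cost is a wording change and one score sheet applied to normal fields that are already on video. No extra patients, procedures or imaging are needed. The small downside is that the tumor-normal contrast may look less striking, because aberrant findings in normal tissue will now count.
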